## Objectives

- Primary objective: determine if daily versus EOD oral iron at the same dose per kilogram per day will achieve similar incidence of iron replete status at 36 weeks PMA.
- Secondary objective:
  - Characterize Ret-Hb levels in preterm infants
  - Identify the number of blood transfusions received between enrollment and 36 weeks' PMA between two groups
  - Determine prevalence of bronchopulmonary dysplasia between two groups
  - Identify the number with sepsis (defined as a positive blood or cerebrospinal fluid culture that was treated with antibiotics for at least 7 days) between two groups
  - Identify the number with necrotizing enterocolitis (NEC)/gastrointestinal perforation (medical NEC defined as  $\geq$ stage II Bell's criteria between two groups
  - Characterize growth (assessed by length gain at 36 weeks' PMA or at discharge if discharged before 36 weeks) between two groups

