### Intervention

- The control group / current standard for iron supplementation in neonates is detailed as follows: after the infant achieves full enteral feeds, the infant is started on 6 mg/kg of oral iron daily supplementation. Though the American Academy of Pediatrics and World Health Recommendation recommend 2 – 4 mg/kg of supplemental iron for premature infants, studies examining the effects of higher dose of enteral iron supplementation (3.4 mg/kg to 7.1 mg/kg per day) revealed no differences between the lower versus higher dosages on morbidity (sepsis, necrotizing enterocolitis, or enteral feeding intolerance) and mortality outcomes. The dose of 6 mg/kg of enteral iron was chosen based on the aforementioned recommendations with evidence of its safety, while minimizing the need to increase the enteral iron dosage if an infant were to be started on ESAs where a dose of 6 mg/kg of enteral iron supplementation is the standard practice. Phlebotomy to obtain a complete blood count, reticulocyte count, and reticulocyte hemoglobin count is pursued the Monday after iron supplementation is started and every 2 weeks thereafter to monitor hematocrit or hemoglobin levels and iron status.

- The intervention group for EOD iron supplementation in neonates is as follows: after the infant achieves full enteral feeds, the infant is started on 6mg/kg of oral iron supplementation administered every other day. Phlebotomy to obtain a complete blood count, reticulocyte count, and reticulocyte hemoglobin count is pursued the Monday after starting iron supplementation and every 2 weeks thereafter to monitor hematocrit or hemoglobin levels and iron status. There is literature revealing that neonates even <29 weeks' gestation absorb and regulate iron similar to adults. There is literature revealing that there is no difference between EOD and daily iron supplementation in older pediatric populations and adults in improving hemoglobin levels, with one study in Switzerland revealing that EOD iron reduced iron deficiency in the longer term and triggered fewer gastrointestinal side effects in adult women. Given the evidence that premature infants regulate their iron status similarly to older infants and adults, and the current evidence of EOD iron in older children and adults, this intervention, compared with our control, will help us address our primary question to determine if EOD iron is non-inferior to daily iron.

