  - Neonatal morbidities documented in the EMR which includes include anemia defined by unit guidelines based on the neonate's clinical status and corrected gestational age, necrotizing enterocolitis, sepsis, chronic lung disease, intubation, death, feeding difficulties
  - Neonatal severity scoring (NSOFA) at start of trial (T0) and every 2 weeks thereafter (T#)
  - Type of feed and calories from T0 to T#
  - Feeding volume at T0 to T#
  - Weekly growth parameters T0 to T# (weight, length, and head circumference)
  - Type of respiratory support T0 to T#
  - Blood draw volume T0 to T#
  - Transfusions from T0 to T#
  - Presence of specific diagnosis: constipation, feeding intolerance, infectious screen, clinical sepsis
- Data collected will include MRN; however, this will not be used in the analysis. All data will be deidentified before they are entered into REDCap for effective safeguard of information. Personnel

identified in this protocol will be responsible for collecting the data and will be the only persons who will have access to the de-identified data inputted on REDCap for further management and analysis.

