## Data Analysis

- A sample size determination was conducted using Riskcalc.org (Chow S-C, Shao J, Wang H, Lokhnygina Y. Sample Size Calculations in Clinical Research. Third ed: Chapman and Hall/CRC; 2017.) and confirmed by [name] (BAMC Statistician). Sample size estimates are for type 1 error of 5% ( $\alpha = 0.05$ ), power ( $1-\beta$ ) of 80%, ratio of 1:1 of intervention to control. The effect size is determined by estimating the proportion of infants with Ret-Hgb >29 pg to be similar at 80% between daily versus EOD iron, with a margin of 20%. It was determined that a sample size of 100 patients would be needed for this study (50 for intervention, and 50 for control).
- A statistician who is blinded to the study allocation will analyze the data. All statistical analyses will be performed with IBM SPSS Statistics (Armonk, NY: IBM Corp) and JASP Team (2022). JASP, Version 0.16.1 (Netherlands: JASP Team). Descriptive statistics will be performed for all variables. Categorical data will be reported as percentages, and continuous data will be reported as medians with interquartile range or means with standard deviation. The two groups will be compared according to the intention to treat with the use of Student's t-tests, Mann-Whitney-U tests, chi-square analysis based on the outcome being evaluated. All p-values will be one-sided, with a statistical significance level of <0.05. Covariates to include gestational age, in-born versus out-born infants, ESA use, receipt of pRBC transfusion will be controlled for using a logistic regression model and will be reported with an odds ratio (OR) and 95% confidence intervals (CI). A medical monitor who is not involved in the study will be assigned prior to the initial enrollment of the trial to monitor the data periodically (every 3 months) to ensure the safety of the participants and the scientific integrity of the study. An interim analysis will be performed at halfway to target enrollment.

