## Identified Risks/Ethical Considerations

- The risks associated with iron deficiency include anemia (and associated symptoms to include tachycardia, tachypnea, increased oxygen requirement, increased apnea/bradycardia/desaturation events which can lead to unnecessary evaluations for sepsis and antibiotic administration), long-term neurodevelopmental impairment, increased risk for necrotizing enterocolitis, packed red blood cell (pRBC) transfusion and transfusion-related risks, as well as delayed growth. The overall risk of iron deficiency will be mitigated by monitoring the complete blood count and reticulocyte count for hemoglobin/hematocrit levels and Ret-Hb levels every two weeks. There is no evidence to suggest EOD

iron dosing will result in worse outcomes compared to daily iron dosing. However, outcomes will be monitored every three months to ensure there are no significant adverse outcomes which would warrant study cessation.

- Current practice for frequency of phlebotomy varies by institution but the recommended frequency of lab draws in this study are within normal standards for preterm infants of this gestational age.
- A medical monitor who is not involved in the study will be assigned prior to the initial enrollment of the trial to monitor the data periodically (every 3 months) to ensure the safety of the participants and the scientific integrity of the study.

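### The sepsis outcome needs at least 7 days of antibiotics, so it omits culture-positive infants who die sooner; death is collected but not named as a between-group outcome

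*Protocol*

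**What the plan says.** Objectives (Protocol) lists the secondary outcomes compared between the two groups: transfusions, bronchopulmonary dysplasia (BPD), sepsis, necrotizing enterocolitis (NEC) or perforation, and growth in length. Ret-Hb levels are also to be characterised. The sepsis item reads "sepsis (defined as a positive blood or cerebrospinal fluid culture that was treated with antibiotics for at least 7 days". Death is not on the list, alone or combined with another outcome.

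Other sections bear on the same event:

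- Data Collection records morbidities from the medical record, including "necrotizing enterocolitis, sepsis, chronic lung disease, intubation, death, feeding difficulties", and separately "Presence of specific diagnosis: constipation, feeding intolerance, infectious screen, clinical sepsis". No 7-day condition is attached to either entry.
- Data Analysis states "Descriptive statistics will be performed for all variables" and "The two groups will be compared according to the intention to treat". It does not list which outcomes are tested.
- Data Analysis assigns an uninvolved medical monitor "to monitor the data periodically (every 3 months) to ensure the safety of the participants", and Identified Risks/Ethical Considerations adds that "outcomes will be monitored every three months to ensure there are no significant adverse outcomes which would warrant study cessation". The monitored outcomes are not named.
- Intervention supports the chosen dose partly with literature that "revealed no differences between the lower versus higher dosages on morbidity (sepsis, necrotizing enterocolitis, or enteral feeding intolerance) and mortality outcomes".

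**The concern.** The definition sets two conditions: a positive culture and a minimum treatment time. An infant can meet the second only by living through that time. A duration rule is a reasonable way to keep contaminated cultures out of the count, but death during treatment is not evidence of contamination. Applied to deaths, the rule removes the most severe true cases and keeps the milder ones.

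The direction of the error is therefore predictable: if sepsis is fatal sooner in one arm, that arm records fewer sepsis cases. What is at stake is the reading of a safety outcome for a dosing schedule whose clinical effect, by the protocol's own Background, has not been studied in this population. The sepsis count needs deaths by arm beside it, and Objectives does not name that comparison.

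**Working it through.** **1. The rule applied to one infant.** Suppose an enrolled infant has a positive blood culture and dies on day 2 of antibiotics.

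| Place in the protocol | Result for this infant |
|---|---|
| Objectives, sepsis | Not a case: 2 days is less than 7 |
| Objectives, death | No such outcome named |
| Objectives, transfusions and NEC/perforation | Counted if they occurred before death |
| Data Collection, death | Recorded |
| Data Collection, sepsis in the medical record, clinical sepsis | May be recorded; no definition given |
| Data Analysis | Death described with all other variables |

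The omission is thus specific to the defined sepsis count. The event stays visible elsewhere, but not as a named between-group outcome.

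**2. Scale of one infant.** Data Analysis gives 50 per arm. That figure reproduces from its stated inputs (80% in both arms, margin 20 points, one-sided 0.05, power 80%):

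n = (1.645 + 0.842)² × (0.8×0.2 + 0.8×0.2) / 0.2² = 6.18 × 0.32 / 0.04 ≈ 49.5, rounded up to 50 per arm, 100 in total.

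One infant is 1/50 = 2 percentage points. The point does not depend on this calculation and does not change it.

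**3. Direction (assumed counts).** With 5 culture-positive infants in each arm, of whom 2 in one arm die before 7 days, the definition reports 3/50 = 6% against 5/50 = 10%. The true counts are equal. This shows the direction only; it is not a forecast.

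**4. How often the rule could bite (assumed rates).** The protocol gives neither a sepsis risk *s* nor a proportion *f* of septic infants who die before 7 days of antibiotics. Taking each from 5% to 20%:

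- cases dropped per arm = 50 × s × f
- chance of at least one dropped case among 100 = 1 − (1 − s×f)^100

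| s | f | Culture-positive cases per arm | Dropped per arm | Chance of at least one in 100 |
|---|---|---|---|---|
| 5% | 5% | 2.5 | 0.125 | 22% |
| 10% | 10% | 5 | 0.5 | 63% |
| 20% | 20% | 10 | 2 | 98% |

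The range is too wide to say more than that the effect could be nil or could be a few infants. A comparison is distorted only in so far as early deaths differ between arms.

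**The case against.** A reader might infer that such a death could vanish from every safety result. The protocol does not support that. Death is a named data item, sepsis in the medical record and clinical sepsis are recorded without the 7-day rule, all variables are to be described, and an independent monitor looks every three months. In the assumed example above, the same report would show 2 deaths against 0. This stands, and limits the point to the defined sepsis count and to the missing mention of death as a compared outcome.

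Nor does the infant appear event-free on the other outcomes. A missing 36-week Ret-Hb or length is missing, and nothing in the protocol scores it as a success. Transfusions and NEC or perforation still count in an infant who later dies.

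It is also tempting to say that an arm with more deaths would show less BPD. Objectives states no assessment time or denominator for BPD, so that claim needs a definition from outside the document. Composite outcomes and the handling of competing events may be set in a statistical analysis plan that is not at hand; their absence here is not a fault.

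The effect may also be small. Study Subjects admits only infants on full enteral feeds who start oral iron, so earlier deaths never enter the trial. The mortality reference in Intervention concerns dose level and commits the trial to no mortality comparison.

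What these arguments do not answer is the definition itself. It is written in the protocol and is complete as it stands. An analysis plan that counted early deaths as sepsis would contradict it.

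**Conclusion.** The point holds in a limited form. Read literally, the sepsis outcome leaves out culture-positive infants who die before completing 7 days of antibiotics, and the between-group count is biased in favour of an arm with more rapidly fatal sepsis. Death is collected and will be described, but is not named among the outcomes compared between groups.

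The size cannot be established from the protocol. Each omitted infant moves an arm by 2 percentage points; the 22% to 98% chance of at least one such infant rests wholly on assumed rates. The conclusion assumes that the duration is counted as treatment actually given, which is what the wording says, and not treatment intended. Only a secondary outcome is affected.

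**What to change.** Amend the sepsis definition in Objectives so that a positive blood or cerebrospinal fluid culture counts if antibiotics were given for at least 7 days, or if the infant died before 7 days of treatment were completed. Add death from randomisation to 36 weeks PMA or discharge, by arm, as a secondary safety outcome, so that the sepsis and BPD counts are read beside it.

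The cost is a protocol wording change and one more row in the safety table. Death is already collected, and neither the sample size nor the treatment of any infant changes. The one drawback is that a contaminated culture in an infant who dies of another cause could now be counted as sepsis. Reporting deaths by arm beside the sepsis count lets a reader judge how much this could matter.

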## Research Question/Hypothesis

- Research Question: Will preterm neonates with estimated gestational age of 26 0/7 to 32 6/7 gestation who are supplemented with iron on an every-other-day (EOD) dosing, compared to those who are supplemented with iron daily, have the same incidence of achieving iron replete status (reticulocyte-Hb >29) at 36 weeks post-menstrual age (PMA)?
- Hypothesis: We hypothesize that at the same dosage in oral form, there will be no difference in the incidence of preterm neonates achieving iron replete status as measured by reticulocyte hemoglobin (Ret-Hb) between EOD and daily iron supplementation.

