### **Study Subjects**

- The population to be studied include premature infants who completed 26 0/7 to 32 6/7 weeks' gestation. We will include premature infants who are on full enteral feeds and are started on oral iron

therapy. Infants with known congenital anomalies or chromosomal abnormalities (such as Trisomy 18 or Trisomy 21), conditions that affect iron metabolism (such as thalassemia or hemochromatosis), bleeding disorders or coagulopathy, and received iron parenterally will be excluded from the study.

- There will be need for a written consent from the patient's' parent or legal guardian. A copy of the written consent will be included in the appendix.
- Our target population are neonates, which fall under the category of special subject population. Literature on the benefits of every other day iron dosing compared with daily iron dosing is already available in older pediatric patients and adults. There have been no studies investigating their benefits in the neonatal population, despite this population being the most vulnerable to iron deficiency and its consequences, as well as emerging evidence that neonate regular iron metabolism similar to adults.

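### Length gain is totalled over windows that differ about 3- to 7-fold between infants and may end at discharge, which costs precision; analyse it per week or as a z-score change

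*Protocol*

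**What the plan says.** **Growth endpoint.** Protocol, Objectives, makes growth a secondary objective, assessed by length gain at 36 weeks' PMA "or at discharge if discharged before 36 weeks". It does not say from when gain is counted, or whether it is per week or standardised for age.

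**Who is observed, and from when.** The research question concerns "preterm neonates with estimated gestational age of 26 0/7 to 32 6/7 gestation". Under Intervention, control infants begin treatment as follows: "after the infant achieves full enteral feeds, the infant is started on 6 mg/kg of oral iron daily supplementation". The every-other-day arm also starts at full feeds. The postnatal age at that point is not given.

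**Analysis.** Data Analysis compares the arms "with the use of Student's t-tests, Mann-Whitney-U tests, chi-square analysis", chosen according to the outcome. Gestational age is listed as a covariate, but for a logistic regression.

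**Data available.** Data Collection lists "Weekly growth parameters T0 to T# (weight, length, and head circumference".

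**Transfusions.** The objective is "Identify the number of blood transfusions received between enrollment and 36 weeks' PMA between two groups". Data Collection instead records transfusions from T0 to T#, and separately a number of red-cell transfusions with no window. T0 is the first blood draw once iron has begun. The laboratory schedule that defines T# stops at 36 weeks PMA or at discharge.

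**The concern.** An infant born at 26 weeks is followed for several times as long as one born at 32 weeks, so much of the spread in total length gain reflects time observed rather than speed of growth. The named tests treat that spread as noise. Randomisation is simple and not stratified by gestational age, so a chance imbalance in windows would also go uncorrected.

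This matters because the Protocol's risk section lists delayed growth among the consequences of iron deficiency. Growth is thus one of the outcomes in which harm from less frequent iron could appear. The trial hypothesises no difference on its primary outcome; an imprecise growth comparison could make a real deficit look like reassurance.

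There is also a conditional route to bias. Discharge follows randomisation. If one arm went home earlier, it would show less total gain even with identical growth.

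**Working it through.** **1. The plan's own figure.** No figure is given for growth. The only sample size is for the primary endpoint: 80% in both arms, margin 20 points, one-sided 0.05, power 80%. It reproduces: n = (1.645 + 0.842)² × (0.8×0.2 + 0.8×0.2) / 0.20² = 6.185 × 8 = 49.5, so 50 per arm. That 50 is used below.

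**2. Window lengths.** Window = 36 − (gestational age + weeks from birth to full feeds). The gestational ages are the Protocol's; the time to full feeds is assumed.

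| Time to full feeds | Born 26 0/7 | Born 32 6/7 | Ratio |
|---|---|---|---|
| 0 (from birth) | 10.0 wk | 3.14 wk | 3.2 |
| 1 week for all | 9.0 | 2.14 | 4.2 |
| 2 weeks for all | 8.0 | 1.14 | 7.0 |
| 3 weeks (youngest), 1 week (oldest) | 7.0 | 2.14 | 3.3 |

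**3. Share of variance due to the window.** Assumptions, none of them in the document: mean growth g = 1.0 cm/week; between-infant SD of growth b = 0.2 to 0.4 cm/week; measurement SD of the gain 0.5 cm; full feeds at 1 week, or at 1 to 3 weeks by gestational age; gestational age uniform or weighted to later weeks; either no early discharge, or 30% of infants born at 30 weeks or later leaving between 34.5 and 36 weeks PMA. Simulations of 300,000 infants per scenario gave the mean and SD of the window W. With these,

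Var(total gain) = g²·Var(W) + b²·(mean² + Var(W)) + 0.5².

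- Highest share (mean W 5.48, SD 2.09, b = 0.2): 4.37 + 0.04×34.40 + 0.25 = 5.99. Share = 4.37/5.99 = 73%.
- Lowest share (mean W 3.83, SD 1.11, b = 0.4): 1.23 + 0.16×15.90 + 0.25 = 4.03. Share = 1.23/4.03 = 31%.

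Variance inflation = 1/(1 − share): 1/0.69 = 1.4 to 1/0.27 = 3.7. Interval width grows by the square root: 1.2 to 1.9.

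**4. Power, 50 per arm, one-sided 0.05, assumed arm difference 0.15 cm/week.** Power = Φ(difference / (SD × √(2/50)) − 1.645), with √(2/50) = 0.2.

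- Mean W 5.48, b = 0.2. Total: 0.822/(2.45×0.2) = 1.68, power 51%. Per week, SD 0.24: simulated power 94%.
- Mean W 5.48, b = 0.4. Total: 0.822/(3.18×0.2) = 1.29, power 36%. Per week, SD 0.42: 0.15/(0.42×0.2) = 1.79, power 56%.

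Across all scenarios, power is 36% to 63% on total gain and 53% to 95% on gain per week.

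**5. Shift if discharge timing differed by arm.** Shift = extra share discharged early × weeks early × 1 cm/week. With 10% to 30% more infants leaving 0.5 to 1.5 weeks early, it runs from 0.10×0.5 = 0.05 cm to 0.30×1.5 = 0.45 cm. The assumed true effect over mean windows of 3.7 to 5.6 weeks is 0.15×3.7 = 0.55 to 0.15×5.6 = 0.84 cm.

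**6. Transfusions.** With Poisson counts at an assumed 0.05, 0.10 or 0.20 per week, window length explains 3%, 5% or 9% of the variance. For a rate ratio of 1.5, power is 31%, 49% and 73% on the count, against about 32%, 51% and 76% with an offset for time at risk.

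**The case against.** **It could be left to a statistical analysis plan.** One may exist, the tests are to be chosen by outcome, and the growth wording does not rule out a weekly scale. This has some force for the choice between velocity and z-score. But the Protocol itself fixes the endpoint as a gain, allows it to end at discharge, and names tests without time or gestational age for a continuous outcome.

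**Gestational age is a planned covariate.** True, and it is the main driver of window length, but the model named is logistic.

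**Every growth input is assumed.** Correct. The document gives no growth rate, SD, time to full feeds or discharge timing, so the size is a range.

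**Stronger readings that the document does not support.**

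- *A 5- to 10-fold variance inflation.* A reader might get this from 1 + (g × 2.02/s)², where 2.02 weeks is the window SD when gestational age is uniform over 26 to 33 weeks and s is a fixed residual SD: 5.1 at g = 1, s = 1, and 10.2 at g = 1.2, s = 0.8. A fixed s ignores that differences in growth rate accumulate over longer windows, and a common time to full feeds ignores that the youngest may take longer.
- *A biased comparison.* Unequal windows alone add noise, because randomisation balances them on average. The Protocol cites fewer gastrointestinal side effects in older populations and a potential benefit here, but nowhere links every-other-day dosing to earlier discharge.
- *Transfusion counts swamped and cut off at discharge.* The objective runs to 36 weeks PMA with no discharge clause; truncation follows only if T# is read as in the laboratory schedule. Chance dominates these counts, and a count to a fixed PMA is a legitimate measure of burden.

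**Conclusion.** The point holds for length gain, as a matter of precision in a secondary endpoint. As written, the comparison mixes growth with observation time over windows differing about 3- to 7-fold. The likely cost is a 1.4- to 3.7-fold variance inflation, under the assumptions in the working. Bias is conditional on discharge before 36 weeks differing by arm; if it did, the shift could be 0.05 to 0.45 cm at 1 cm/week. For transfusions the only defect is that the objective and the data-collection list describe different windows. The sample size and primary conclusion are untouched, so this is a worthwhile improvement rather than a serious flaw.

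**What to change.** **Growth.** State the start point, for example T0. Analyse length gain per week from there to the last measurement, or change in PMA-specific length z-score with the reference chart named. Use a linear model with arm, gestational age and starting length.

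The small downside is that velocities from very short windows are noisy: a 0.5 cm measurement SD is 0.5/2.14 = 0.23 cm/week over the shortest one-week-lag window, against 0.5/9 = 0.06 over the longest.

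**Transfusions.** Give one window in both Objectives and Data Collection, with the same start (enrollment or T0) and an explicit end for infants discharged early. An offset for time at risk is optional and gains only 1 to 3 points of power.

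**Cost.** Wording only. Weekly lengths are already to be collected, so no new data are needed.
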